1.0 Background

MOSES technology was developed by Lumenis Ltd to maximize the lithotripsy potential of high powered lasers. Typically, a holmium laser unit is used to treat kidney and ureteral stones that are too large to remove en block. Laser lithotripsy allows for a large stone to be partitioned into smaller fragments that can be removed with an endoscopic basket device. Holmium technology has existed for more than 20 years, however, low total power (40 watt) and minimal modulations (Joules and Hertz) of the laser energy by the laser units limited the capacity to improve lithotripsy efficiency.

With the advent of high power (120 watt) lasers with 4 laser cores and developments in software to modulate the laser energy, many more options have emerged for laser lithotripsy of kidney and ureteral stones. At our institution, the laser units used for nephrolithotripsy are engineered and produced by Lumenis Ltd. These units are fitted with MOSES technology. Standard laser lithotripsy or MOSES laser lithotripsy can be performed using the same unit and during the same case by simple turning MOSES on or off on the laser touch screen (image 1). MOSES is propriety technology that is software based modulation of the laser energy delivered from the holmium:yag laser source. The software changes the pulsed laser to have two peaks of energy – one to displace the water in front of the stone and the second to deliver the laser energy to the stone. Holmium laser energy dissipates quickly in water, so the displacement of water in front of the stone means more energy is delivered to the stone. With more energy delivery, we would expect stone fragmentation to occur more rapidly.

When treating kidney or ureteral stones, there are two distinct surgical approaches. One technique is to use laser lithotripsy to break a stone into tiny pieces called *dusting*. Dusting technique attempts to turn a stone into a slurry of 2mm or less stone fragments that the patient can pass spontaneously. There are some urologist who promote the use of MOSES technology to improve the efficiency of the dusting technique and reduce operative time. Another approach to endoscopic stone surgery is to laser the stone into fragments to remove with a basket. There is far less laser energy used in this process, however, hard stones and larger stones can take time to fragment. We feel, based on the dusting ureteroscopy data, that MOSES technology could still improve fragmentation efficiency and reduce overall operative time.

2.0 Rationale and Specific Aims

To determine the effects of MOSES laser modulation technology can improve the safety and efficiency to laser fragmentation resulting in decreased total laser time, reduced potential for injury to the patient, and total OR time and utilization.

3.0 Inclusion/Exclusion Criteria

Inclusion criteria:

- >18 years of age
- Kidney or ureteral stone requiring laser lithotripsy fragmentation

Exclusion criteria:

- < 18 years of age

- Infectious, struvite stones.
- Atypical collecting system anatomy that prolongs the case (ureteral stricture, malrotated kidney, infundibular stenosis, ureteral duplication)

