4.0 Enrollment/Randomization

Potential subjects will be identified during their pre-operative clinic visit. Physician-investigators will review medical chart and relevant pre-operative testing to make this determination. Potential subjects will then meet with a member of the study team to read the consent in detail and discuss the study in full.

After consent has been obtained, the study personnel obtaining consent will then obtain and assign the appropriate randomization for that subject. The patients will be randomized 1:1 to either standard laser lithotripsy or MOSES laser lithotripsy. Randomization will be performed using the redcap randomization application.

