7.0 Study Withdrawal/Discontinuation

If a subject wishes to withdraw from the study, he may do so by verbal or written request to the research team. A subject may be withdrawn from the study by a physician-investigator if determined to be in the subject's best interest for medical reasons.

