8.0 Statistical Considerations

Overall OR duration may differ up to 10 min with an average OR time for URS estimated at approximately 1 hour. A power analysis with 80% power and an alpha of 0.05 requires a total recruitment of 106 patients with 53 patients in each treatment arm. Due to a 10% chance of withdrawal rate, the study will enroll 116 subjects for 106 subjects to complete the study. Statistical analysis of the obtained data will include a student T-test for comparison of two continuous variables and chi-squared for categorical variables. If enough events occur to warrant a multivariate analysis, a Cox regression utilizing forward selection will be performed.

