8.1 Endpoint Considerations

The primary endpoint of interest will reduction in total laser time and total OR time. Secondary endpoints will evaluate complication rates using the Clavien-Dindo score.

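### Does tying the anatomy exclusion to a prolonged case let patients be excluded on the basis of OR time, a primary endpoint?

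*Protocol*

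**What the plan says.** Section 3.0 excludes "Atypical collecting system anatomy that prolongs the case" and adds in parentheses "ureteral stricture, malrotated kidney, infundibular stenosis, ureteral duplication". It gives no time threshold.

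Section 4.0 places identification of subjects at the pre-operative clinic visit and says "Physician-investigators will review medical chart and relevant pre-operative testing to make this determination". Randomization comes later: "After consent has been obtained, the study personnel obtaining consent will then obtain and assign the appropriate randomization for that subject".

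Section 7.0 gives two ways out of the study: the subject's own request, and withdrawal by a physician-investigator in the subject's "best interest for medical reasons".

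Section 8.1 states "The primary endpoint of interest will reduction in total laser time and total OR time". Section 8.0 bases the sample size on OR time: "Overall OR duration may differ up to 10 min with an average OR time for URS estimated at approximately 1 hour", with 80% power, alpha 0.05 and 53 patients per arm. It adds that "the study will enroll 116 subjects for 106 subjects to complete the study".

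**The concern.** Eligibility should rest on what is known before randomization. Whether anatomy has lengthened an operation is known only during or after it, and that length is nearly the same quantity as total OR time. The protocol does not state that eligibility is fixed at randomization, nor what happens when one of these conditions is first seen in surgery. On a literal reading, a randomized patient with newly found anatomy could be declared ineligible because the operation was long, and kept if it was short.

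That would be selection on the outcome. If MOSES shortens cases, more standard-arm than MOSES patients would cross any fixed limit, even if the person deciding did not know the arm. The standard arm would lose more of its long cases and the OR-time difference would shrink.

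**Working it through.** **Reading the sections together.** The four items in parentheses are anatomical states, not durations, and can be looked for on pre-operative imaging and in the history. Section 4.0 says who judges eligibility, from what, and before which step; the sources it names cannot contain the length of an operation not yet done. The protocol describes no eligibility re-check after randomization and no exclusion step in the operating room. A long case fits neither exit in section 7.0. The harmful practice therefore has to be brought in from outside the text.

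**The plan's own figure.** No SD is stated. Solving 80% power for a 10-minute difference, two-sided 0.05, 53 per arm:
- normal approximation: SD = 10 × √(53/2) / (1.960 + 0.842) = 18.4 min;
- noncentral t: SD = 18.2 min, used below.

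**Size if long cases were dropped anyway.** From the protocol: a mean of about 60 min, a difference of 10 min, 53 per arm to complete, and 116/2 = 58 per arm enrolled. Assumed, because the protocol gives none of these: normal OR times with means 60 (standard) and 50 (MOSES); a fraction p with anatomy missed before surgery, adding D minutes; such a patient dropped, without knowledge of arm, if OR time exceeds c.

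For an arm with mean μ, let a = (c − μ − D)/SD.
- Fraction dropped = p × [1 − Φ(a)].
- Mean of the atypical patients who stay = μ + D − SD × φ(a)/Φ(a).
- Their weight = pΦ(a) / [1 − p + pΦ(a)].

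Worked case, p = 0.10, D = 15, c = 75:
- Standard: a = (75 − 75)/18.2 = 0, Φ = 0.500. Dropped 0.10 × 0.500 = 5.0%. Atypical patients who stay average 60.5 min with weight 0.05/0.95 = 0.053. Arm mean 60.02.
- MOSES: a = (75 − 65)/18.2 = 0.549, Φ = 0.709. Dropped 0.10 × 0.291 = 2.9%. Atypical patients who stay average 56.2 min with weight 0.0709/0.9709 = 0.073. Arm mean 50.45.
- Difference = 60.02 − 50.45 = 9.57 min instead of 10.

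All cases at c = 75 (power by noncentral t, starting n reduced by those dropped, no other losses):

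| p | D (min) | Dropped, standard / MOSES | Effect (min) | Power, 53 per arm: dropped / kept | Power, 58 per arm: dropped / kept |
|---|---|---|---|---|---|
| 2% | 15 | 1.0% / 0.6% | 9.92 | 79.3% / 79.5% | 82.8% / 83.0% |
| 5% | 15 | 2.5% / 1.5% | 9.79 | 78.1% / 78.7% | 81.7% / 82.3% |
| 10% | 15 | 5.0% / 2.9% | 9.57 | 76.1% / 77.6% | 79.8% / 81.3% |
| 10% | 30 | 8.0% / 6.1% | 9.60 | 74.2% / 70.9% | 78.0% / 74.8% |

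Varying the cut-off at p = 10%: with D = 15, the effect is 9.77 (c = 65), 9.57 (75) and 9.59 (90). With D = 30 it is 9.86, 9.60 and 9.27.

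A simulation with 58 per arm, SD 18.3, c = 75 and a more extreme 20% missed anatomy gives 9.1 to 9.3 min for 10 to 30 added minutes.

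**No treatment effect.** Arm-blind dropping then acts alike in both arms. Over 40,000 simulated trials per scenario (p from 2% to 10%, D of 15 or 30, c = 75, 53 or 58 per arm), type I error was 0.048 to 0.051.

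**The case for a change.** The best argument for a change is that eligibility wording belongs in the protocol, not the SAP, and that this wording adds an outcome-based qualifier to a list that would work without it. Removing four words and adding about two sentences would close the route before any data exist. Section 8.0 also does not say whether a patient found ineligible late counts among the 106 completers. And the reassurance about type I error needs an arm-blind decision: section 5.0 blinds surgeons, but OR staff know the assignment and the circulating team records OR time, and the protocol does not say who would decide a late exclusion.

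Part of this stands. The qualifier is loosely worded, and deleting it would be a fair editorial tidy-up. The protocol does not guarantee that a late exclusion would be blind. But that argument presupposes late exclusions, which no section provides for. The useful part of the added text, keeping such patients in the analysis as randomized, concerns analysis populations and is commonly SAP content. The edit is also not free of consequences. If the four conditions are examples, making them the whole definition changes who may enrol. With 10% missed anatomy, 30 added minutes and a 75-minute cut-off, keeping the patients gives 71% power against 74% with exclusion, about 3 points lost to remove a bias of 0.4 min.

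**Conclusion.** The concern does not call for a change. Followed as written, the protocol settles eligibility before randomization on named anatomy and gives no ground for dropping a patient after a long operation. What remains is an imprecise qualifier and a gap about late-found anatomy that analysts would ordinarily fill by analysing patients as randomized.

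If the literal reading were acted on without knowledge of the arm, the shift would be about 0.1 to 0.4 min out of 10 in the central cases (2% to 10% missed anatomy, 15 added minutes, 75-minute cut-off). It would be about 0.7 min with 10% missed anatomy, 30 added minutes and a 90-minute cut-off, and up to about 0.9 min at 20% missed anatomy. The shift is toward no difference, so it would not create a false claim of benefit. These sizes rest on an SD solved backwards from the stated sample size and on assumed rates, added minutes, cut-offs and exclusion practice, none of which the protocol gives.

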4.0 Enrollment/Randomization

Potential subjects will be identified during their pre-operative clinic visit. Physician-investigators will review medical chart and relevant pre-operative testing to make this determination. Potential subjects will then meet with a member of the study team to read the consent in detail and discuss the study in full.

After consent has been obtained, the study personnel obtaining consent will then obtain and assign the appropriate randomization for that subject. The patients will be randomized 1:1 to either standard laser lithotripsy or MOSES laser lithotripsy. Randomization will be performed using the redcap randomization application.

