5.0 Study Procedures

This is a blinded study. Our research coordinator will present to the OR prior to the surgeon to meet with OR staff. At this time, the coordinator will inform the OR staff which group the patient has been randomly assigned. OR staff will be educated to set the laser as instructed by the surgeon but not share whether the MOSES laser lithotripsy is being used. Surgeons will not be aware of the group assignment. The surgeons are only able to adjust the laser energy settings between 0.4-1.0 joules and 4-15 hertz. To control for stone fragment size, surgeons will have to use an 13 french ureteral access sheath independent of ureteral diameter. The MOSES setting is turned on with a touch pad attached to the laser unit. Once the surgeon is ready to laser fragment the stone, they will request that the laser be activated and provide the laser energy settings. The laser technician/nurse will follow randomization and add or remove the MOSES option. The surgeons will not be informed if they are using standard laser or MOSES augmented laser technology. At the conclusion of laser fragmentation, stone basket extraction will occur and once all fragments are removed, the patient will have a ureteral stent placed, awoken, extubated and transferred to the post anesthesia recovery unit. Objective data about laser settings, utilization time and total energy will be obtained at the conclusion of the case. Additionally, the circulating team will record the total OR time. Other variables of interest include blood loss, blood transfusion requirements and complications (utilizing Clavien-Dindo classification) with an expected rate of approximately 1-2%. Subjective grading of stone movement during laser fragmentation as well as stone migration will be recorded.

In addition to the intraoperative variables mentioned above, we will obtain clinical information including stone size, location, and stone analysis will be recorded.

6.0 Reporting of Adverse Events or Unanticipated Problems involving Risk to Participants or Others

All adverse events or unanticipated problems related to study participation will be reported in keeping with the IRB's guidelines regarding such events.

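### Randomisation follows consent, before the need for the laser is confirmed in the OR, so avoidable losses fall after allocation while study staff know the arm

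*Protocol*

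**What the plan says.** **Timing of randomisation (Protocol 4.0).** "Potential subjects will be identified during their pre-operative clinic visit". Eligibility is then judged from records: "Physician-investigators will review medical chart and relevant pre-operative testing to make this determination". Next comes "After consent has been obtained, the study personnel obtaining consent will then obtain and assign the appropriate randomization for that subject". The allocation is simple: "The patients will be randomized 1:1 to either standard laser lithotripsy or MOSES laser lithotripsy". No day or place is given for the randomisation, and no day-of-surgery or intraoperative check precedes it.

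**Eligibility (Protocol 3.0).** The stone criterion is "Kidney or ureteral stone requiring laser lithotripsy fragmentation". Struvite stones, and atypical anatomy that lengthens the case, are excluded.

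**When the arms diverge (Protocol 5.0).** "Our research coordinator will present to the OR prior to the surgeon to meet with OR staff", and the coordinator tells those staff the arm. MOSES is added or left off at a touch pad when the surgeon asks for the laser. The surgeon is not told which is in use. Laser data and total OR time are collected at the end of the case.

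**Endpoints (Protocol 8.1).** The primary endpoints are total laser time and total OR time.

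**Losses (Protocol 7.0 and 8.0).** "A subject may be withdrawn from the study by a physician-investigator if determined to be in the subject's best interest for medical reasons". On numbers: "Due to a 10% chance of withdrawal rate, the study will enroll 116 subjects for 106 subjects to complete the study".

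**The concern.** Treatment and both primary outcomes fall within one operation, and the arms are identical until the laser is switched on. Nothing arm-specific has to be prepared beforehand, because MOSES is a setting on the same unit. Randomising earlier therefore buys nothing, and it turns everything that goes wrong between consent and lasering into a post-randomisation loss. That includes withdrawal of consent, cancellation, and an operation in which the stone proves not to need, or not to permit, lasering.

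Such patients then present an awkward choice. If they are kept, they carry no treatment contrast and dilute the comparison, and their laser time is zero or undefined. If they are dropped, the analysis rests on a subset formed after allocation was known to part of the study team. A statistical analysis plan can choose between these, but it cannot move the point of randomisation, which section 4.0 fixes.

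**Working it through.** **Step 1. Sequence set side by side.**
- Identification: clinic visit (4.0).
- Eligibility: chart and pre-operative tests (4.0).
- Consent, then allocation, by the same person (4.0).
- Coordinator, then OR staff, know the arm before the surgeon arrives (5.0).
- Arms first differ: laser request (5.0).
- Primary endpoints complete: end of the operation (5.0, 8.1).

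Any loss between the third and fifth lines is post-randomisation, and nothing in the trial treatment requires it to be.

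**Step 2. The plan's own figure.** Inputs from 8.0: 106 completers, 10% withdrawal, 116 enrolled.
- 106 / (1 − 0.10) = 117.8, rounded up to 118. The stated 116 is two short, which is immaterial.
- 116 × 0.90 = 104.4, so a true 10% loss leaves about 104 patients.

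**Step 3. Implied SD.** Section 8.0 gives a 10 min difference, 53 per arm, 80% power and alpha 0.05, but no SD and no sidedness. I assume a two-sided test.
- Normal approximation: SD = 10 × √(53/2) / (1.960 + 0.842) = 51.48 / 2.802 = 18.4 min.
- With the t distribution: standardised difference 0.549, so SD = 10 / 0.549 = 18.2 min.
- If the test were one-sided, the normal approximation would give 20.7 min.

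**Step 4. Never-lasered patients kept in their arm.** The protocol gives no such rate, so a share p is assumed. Difference = 10 × (1 − p), SD held fixed, n = 58 per arm. In the normal form, power = Φ(difference / (SD × √(2/58)) − 1.960), with SD × √(2/58) = 18.37 × 0.1857 = 3.41 min.

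| p | Difference (min) | Calculation | Power |
|---|---|---|---|
| 0% | 10.0 | Φ(2.93 − 1.96) | 83% |
| 5% | 9.5 | Φ(2.78 − 1.96) | 80% |
| 10% | 9.0 | Φ(2.64 − 1.96) | 75% |
| 20% | 8.0 | Φ(2.34 − 1.96) | 65% |

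The t-based calculation with SD 18.2 agrees to the nearest percentage point.

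**Step 5. Lost patients dropped.** Difference stays 10 min and n falls.

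| Loss | Patients left | Power |
|---|---|---|
| 5% | 110 | about 82% |
| 10% | 104 | 79% |
| 15% | 99 | 77% |
| 20% | 93 | about 75% |

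At the planned 10%, dropping costs almost no power relative to the 80% target. What it costs is the guarantee that the arms compared are the arms randomised.

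**The case against.** The strongest reply is that this is a design preference and not an error. Randomising after consent through REDCap is ordinary practice, and the 116 was chosen to absorb a 10% loss. The causes of loss are also conjecture: the protocol does not say why patients would withdraw, and it names no passed stones or cancelled operations as expected events. All of that stands, and it limits the claim. It does not answer why allocation should precede the point at which it is needed, in a trial whose primary outcomes require no follow-up.

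Four stronger readings are tempting, and the protocol does not support them.

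- **That nobody knows at randomisation whether the stone will be lasered.** Need for laser fragmentation is an inclusion criterion, and physician-investigators judge it beforehand. Only confirmation in the OR is missing.
- **That 10% of patients will not be lasered.** The 10% in 8.0 is a withdrawal rate without a stated cause. Using it as a never-lasered rate is an assumption. Applying 10% dilution and also shrinking the trial to 53 per arm would count two losses where the protocol plans one.
- **That someone able to withdraw a patient knows the arm.** Section 4.0 has a member of the study team go through consent. Section 5.0 blinds the surgeon, and 7.0 limits investigator withdrawal to medical reasons. Nothing shows that the two roles overlap, though nothing rules it out.
- **That later randomisation brings losses close to zero, so that 106 randomised patients suffice.** Randomising before the staff briefing leaves the intraoperative losses in place. Struvite identified by later stone analysis remains under any timing.

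The dilution model is also simple. It holds the SD fixed, and it covers OR time only, since 8.0 gives no planning figures for laser time.

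**Conclusion.** The point holds as an inexpensive improvement to the design. Section 4.0 places randomisation earlier than the treatment requires, so avoidable losses fall after allocation while the person who took consent, and later the coordinator and OR staff, know the arm. That randomisation takes place at or soon after the clinic visit is the natural reading of the sequence, but no date is stated.

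The effect on power is modest: a few percentage points either side of the 80% target under assumed losses of 5% to 10%. These figures rest on a two-sided test, a back-calculated SD and a loss rate that the protocol does not supply. The main benefit is a comparison less exposed to post-allocation selection and dilution, and that benefit cannot be quantified from the protocol. How randomised but never-lasered patients will be analysed may be settled in a statistical analysis plan that is not shown, so its absence from the protocol is not part of this finding.

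**What to change.** In 4.0, keep consent in clinic and move the REDCap randomisation later. There are two options.

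1. The coordinator randomises on the day of surgery, just before briefing the OR staff. This removes losses that occur before surgery and fits the existing procedure, since the coordinator already attends ahead of the surgeon.
2. The laser technician or coordinator opens the assignment when the laser is requested, out of the surgeon's sight. This also removes most intraoperative losses.

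With either option, state that every patient randomised at that point is analysed as randomised. In 8.0, apply the 10% allowance mainly to consented rather than randomised patients. Under option 1, keep some allowance for intraoperative losses.

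The cost is a short amendment and REDCap access in or near the OR on the day. Option 2 also adds a brief step inside total OR time, a primary endpoint. The step is the same in both arms, but it must be handled so that the surgeon stays blinded. No extra patients or procedures are needed. Neither option deals with struvite found on later stone analysis.
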